## Specific Aims and Hypotheses

### Aim 1.

The principle aim of our proposed clinical trial is whether an enhanced *mHealth care management model* with connected health technology used in partnership with the healthcare system team, an older person with heart failure (HF), and their caregiver are more effective than a *provider directed management model* using non-connected home equipment kits. Self-care of HF, quality of life and quality care are represented by multiple outcome measures that are important to patients, caregivers and healthcare (HC) systems. Specifically,

**Aim 1a. Patient-centered outcome measures:** We hypothesize that the mHealth model will increase measures from baseline to 3- and 6-month for the primary outcome of self-care management of HF compared to the provider-directed model. Further, we hypothesize that the mHealth model will increase measures from baseline to 3- and 6-month for secondary outcomes of Self-efficacy to manage symptoms, medications, & treatments; self-care confidence; physical function, sleep, social roles, (Promis 43v2.1 Health profile); heart failure knowledge; satisfaction with care; quality of life; informational support and equipment usability (3 and 6 months), while decreasing health distress, anxiety, depression, fatigue, and pain compared to the provider-directed model.

**Aim 1b. Caregiver outcome measures:** We hypothesize that the mHealth model will reduce caregiver burden, while increasing caregiver health compared to the provider-directed model from baseline to 6-months.

**Aim 1c. Health system outcome measures:** We hypothesize that the mHealth model will reduce hospital admissions, 1-month readmissions, emergency department

Study Title: Innovative Care of Older Adults with Chronic Heart Failure (I-COACH): A Comparative Effectiveness Clinical Trial  
PI (researcher): [name], RD  
Institution: University of Arkansas for Medical Sciences  
Funding: PCORI Grant

visits, and 6-month mortality of HF participants while increasing satisfaction with care, compared to the provider-directed model.

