2	St. Louis University Mental Status (SLUMS) Examination 	Secondary Outcome: Patient Characteristic	Cognitive assessment (OBJECTIVE MEASURE)	X			10 min.
2	Patient Demographics (self-report & medical record review)	Secondary Outcome: Patient Characteristics:	Education, income, rurality, HF severity, years diagnosed, caregiver location, etc	X			5 min.
1a	Minnesota Living with HF (MLHFQ) 	Secondary & Long-Term Outcome	Assesses Quality of Life	X		X	5-10 min.
2	Newest Vital Sign 	Secondary Outcome: Patient Characteristics	Screens for Health Literacy	X			5 min.
CAREGIVER CENTERED OUTCOME MEASURES							
1b	Caregiver Burden 	Secondary Outcome	Assess caregiver perception of burden	X		X	30 min.
1b	Optum®SF-36® v2 Health Survey 	Secondary Outcome	Health domains- Functional Psych. Health & Well-being	X		X	5-10 min
PROVIDER & HEALTH SYSTEM MEASURES							
1c	Satisfaction with Care 	Secondary Outcome	Patient assesses satisfaction with care	X	X	X	1-3 min
1c & 2	Hospital, Emergency Visits, Provider Visits, Mortality	Secondary Outcome	Counts from Medical Record	X	X	X	N/A

Study Title: Innovative Care of Older Adults with Chronic Heart Failure (I-COACH): A Comparative Effectiveness Clinical Trial  
PI (researcher): [name], RD  
Institution: University of Arkansas for Medical Sciences  
Funding: PCORI Grant

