## **Data Analysis**

Data will be examined for completeness, outliers, and normality. Frequencies and percentages will be generated for screen failure reasons, for randomized participants, reasons for dropout and missing data. Descriptive statistics will be generated by intervention assignment and overall at 3 and 6 months. Baseline patient, caregiver, and system level characteristics will be compared according to intervention assignment to assess the success of the randomization; if there are imbalances, then consideration will be given to including the specific characteristic as a covariate to adjust intervention group comparisons. Continuous baseline variables will be compared using two-sample t-tests or nonparametric Wilcoxon rank sum & categorical variables will be compared using chi-square or Fisher's exact test.

Study Title: Innovative Care of Older Adults with Chronic Heart Failure (I-COACH): A

Comparative Effectiveness Clinical Trial

PI (researcher): [name], RD

Institution: University of Arkansas for Medical Sciences

Funding: PCORI Grant

For the Primary Outcome (Self-Care of Heart Failure Index, management subscale, Aim 1), we plan to compare arms in terms of change from baseline using a repeated measures mixed model analysis of covariance (ANCOVA) with an interaction between time and adjusting for baseline subscale score and other covariates such as age, race, education, and rurality. To address correlation arising from repeated measurements on the same subject over time, a random subject effect will be included in the model. For the primary endpoint, we will compare intervention effect at 3 months and at 6 months using contrasts (model-based t-tests) at a significance level of 0.025 (Bonferroni adjustment of alpha level of 0.05 for 2 comparisons). We will also use multiple imputation methods to address missing data (see below). Since scores  $> 70$  on the standardized scale have been used to indicate adequacy of self-care using a similar approach to the above, we will also analyze data as a binary endpoint in a repeated measures logistic model based on a generalized linear model framework.

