Secondary Outcomes, including other patient centered, caregiver, and health system outcomes, will similarly be modeled using an ANCOVA approach. Hospital admissions and adverse events will be analyzed as proportion with unplanned admissions in the next 6 months and event rates using logistic models and models based on Poisson calculations or Negative Binomial to handle potential over-dispersion issues, and mortality and time to first unplanned hospitalization will be compared using survival methods such as log-rank tests and Cox proportional hazards models.

Evaluating heterogeneity of the treatment effect is a key consideration for Aim 2 since we want to identify which patients benefit most. The objective of the HTE analyses is evaluate whether the interventions produce differential benefits for subsets of participants. This will be investigated by including an interaction between baseline factors and intervention group (i.e., race x group) to the model above, and comparisons made using contrasts (model-based t-tests). The analytical approach taken is known as moderator analysis. Baseline factors include the demographic information as well as others measures, such as baseline self-care management score, age, race, rurality, gender, education, time since initial HF diagnosis, HF severity, depression, self-care confidence, etc. Factors with small subgroups ( $<20\%$  of the sample size) will not be investigated. If the arm x time interaction is significant, we will include 3-way interactions to investigate if the intervention effect differs by subgroup at each time point. When there is not a significant interaction with time, we will investigate how the arm effect differs for subgroups averaged across time. The proposed measures will be considered moderators if it meets the eligibility and analytic criteria described by Wang & Ware (2013). Using the model mentioned above, we will also analyze data as a binary endpoint (adequacy of self-care  $>70$  vs.  $<70$ ) in a repeated measures logistic model; with this approach we can also give the probability of achieving adequacy of self-care for various subgroups in addition to odds ratios.

Study Title: Innovative Care of Older Adults with Chronic Heart Failure (I-COACH): A

Comparative Effectiveness Clinical Trial

PI (researcher): [name], RD

Institution: University of Arkansas for Medical Sciences

Funding: PCORI Grant

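### Emergency department visits and provider visits default to ANCOVA with no allowance for time at risk, which biases the comparison if mortality differs between arms

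*Combined protocol and SAP*

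**What the plan says.** The relevant text is in the Data Analysis section of the combined protocol and SAP.

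- **Default rule.** The rule covers secondary outcomes generally and names the group at issue here: "health system outcomes, will similarly be modeled using an ANCOVA approach". The word *similarly* points back to the primary analysis, which will "compare arms in terms of change from baseline using a repeated measures mixed model analysis of covariance (ANCOVA") with baseline adjustment.
- **First exception.** "Hospital admissions and adverse events will be analyzed as proportion with unplanned admissions in the next 6 months and event rates using logistic models", together with "models based on Poisson calculations or Negative Binomial to handle potential over-dispersion issues".
- **Second exception.** "mortality and time to first unplanned hospitalization will be compared using survival methods".

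The outcomes at issue are defined elsewhere. Aim 1c hypothesises that mHealth will "reduce hospital admissions, 1-month readmissions, emergency department" visits and six-month mortality. Table 1 lists hospital, emergency and provider visits and mortality as secondary outcomes at baseline, 3 and 6 months, described as "Counts from Medical Record".

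Neither exception names ED visits or provider visits. No section mentions an offset or person-time. The reference to event rates for admissions implies a denominator but does not define one.

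**The concern.** ED and provider visits accumulate over time. A patient who dies in the first month has had little time to make any visits, and a raw count makes that patient look like a low user. ANCOVA on such counts has no term that separates few visits from little time.

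This would not matter if deaths were rare or balanced. The plan expects up to 10% of patients to die by six months, and Aim 1c hypothesises fewer deaths under mHealth. The missing-data text also commits to using data from everyone randomised. If the mortality hypothesis is true, mHealth patients are observed longer and accumulate more visits, so success on one Aim 1c outcome would partly hide success on another. Aim 1c states no direction for provider visits, but the same distortion would apply.

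**Working it through.** The plan gives no power, event rate, dispersion or effect size for these outcomes, so there is no figure of its own to reproduce.

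**Inputs from the documents.** 400 patients (Study Population); up to 10% deaths by six months (Data Analysis, missing data).

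**Assumed, because the documents do not give them.** 200 patients per arm; two-sided 0.05 for secondary outcomes; the split of deaths by arm; deaths uniform over six months and independent of visit rate; visit rates, dispersion and true rate ratios as shown below.

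**Step 1: bias in the ratio of raw mean counts.** If a proportion *d* dies uniformly over follow-up, mean exposure is 1 − *d*/2. The ratio of raw means is then

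RR × (1 − *d*_mHealth/2) / (1 − *d*_control/2).

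With no true effect (RR = 1):

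- 10% vs 10%: 0.95/0.95 = 1.00
- 8% vs 12%: 0.96/0.94 = 1.021
- 6% vs 14%: 0.97/0.93 = 1.043
- 5% vs 15%: 0.975/0.925 = 1.054

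The bias runs against the arm with better survival. A true ratio of 0.70 would appear as 0.70 × 1.021 = 0.715 or 0.70 × 1.054 = 0.738.

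**Step 2: power and type I error by simulation.** Gamma-Poisson counts were stopped at death, with 1,000 runs per cell. ANCOVA was least squares on the six-month count, adjusted for the prior count; using change from baseline instead would give the same arm coefficient. The comparator was negative binomial (NB) regression with log time as offset, log(1 + prior count) as covariate and robust standard errors. The Monte Carlo standard error is at most √(0.5 × 0.5/1000) = 1.6 points for power and about √(0.05 × 0.95/1000) = 0.7 points for type I error.

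Power (%), ANCOVA on raw counts vs NB with offset:

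| Control mean visits, dispersion, true ratio | 10% vs 10% deaths | 8% vs 12% | 5% vs 15% |
|---|---|---|---|
| 0.6, 1.0, 0.70 | 55.2 vs 55.0 | 48.3 vs 55.2 | 42.8 vs 56.4 |
| 1.0, 1.0, 0.70 | 74.7 vs 73.0 | 68.1 vs 73.9 | 64.2 vs 77.9 |
| 4.0, 0.5, 0.80 | 89.2 vs 90.8 | 78.6 vs 87.8 | 65.5 vs 88.7 |

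The losses are 6.9, 5.8 and 9.2 points at 8% vs 12%, and 13.6, 13.7 and 23.2 points at 5% vs 15%. At equal mortality the methods differ by less than 2 points in either direction.

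Type I error (%), same order of rows:

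| Control mean visits | ANCOVA, 8% vs 12% | ANCOVA, 5% vs 15% | NB with offset, 5% vs 15% |
|---|---|---|---|
| 0.6 | 4.6 | 6.6 | 6.5 |
| 1.0 | 5.1 | 8.0 | 5.0 |
| 4.0 | 5.8 | 10.8 | 5.0 |

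With the offset, the estimated ratio (taken from a Poisson fit with the same offset) stayed at 0.69 to 0.70 and at 0.80, as assumed.

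A further set of runs at about 10% overall mortality gave losses of about 1 to 7 points at 8% vs 12% and 11 to 20 points at 5% vs 15%, with type I error of 6% to 10% at the latter. Together the ranges are 1 to 9 and 11 to 23 points.

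**Step 3: is ANCOVA itself the fault?** When ANCOVA was run in six-month survivors only, power was within 3 points of the offset model in every cell (for example 52.3% vs 55.2%, and 88.4% vs 88.7%). The damage comes from ignoring time at risk, not from the linear model.

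**The case against.** **The handling of deaths is not stated.** The plan's model is a repeated-measures mixed model, with multiple imputation for missing data. The simulation uses a single count and treats a patient's count up to death as complete. The documents do not say that this is what would be done, and a survivors-only analysis would lose little power under the assumptions used. This stands as a condition on the result. It is not a defence of the text, because leaving out patients who died would conflict with the stated intent-to-treat approach.

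**Other provisions might help.** The sensitivity paragraph offers transformations and rank or robust methods, but for continuous endpoints, and none of these supplies exposure time. The composite approach for differential dropout is modelled on quality-of-life outcomes and is not tied to visit counts. Neither repairs the gap.

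**Stronger readings that a reader might infer.**

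- *That 1-month readmission is also assigned to ANCOVA and loses power.* A readmission can be read as a hospital admission, for which logistic models are planned, so the text is ambiguous at most. A linear model also costs almost nothing there: 59.7% vs 59.4% power for assumed risks of 20% vs 12%, and 69.9% vs 69.4% for 25% vs 15%.
- *That a real reduction could be reversed.* Step 1 shows attenuation only: 0.70 becomes 0.738 in the most uneven case considered.
- *That larger harm is likely.* A split such as 18% vs 8% averages 13% deaths, above the plan's expected ceiling. Even 5% vs 15% is a threefold difference that no passage supports.

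**Conclusion.** The point holds for ED visits and provider visits. As written, both are analysed by ANCOVA with no allowance for time at risk, and the count models planned for admissions share the missing offset. Moving the two outcomes into that sentence would therefore not be enough.

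The harm depends on a mortality difference and on using the shortened counts of patients who die as they stand. At about 10% overall mortality it is small to moderate for 8% vs 12% deaths (about 2% on the ratio, 1 to 9 points of power, type I error near nominal). It is larger for 5% vs 15% (about 5%, 11 to 23 points, type I error of roughly 6% to 11%). It is immaterial at equal mortality. These sizes rest on assumed rates, dispersion, allocation and mortality splits, and on deaths unrelated to visit rate in the tabulated runs. The outcomes are secondary, and the primary analysis is untouched. The change is worth making because ED visits are a hypothesised outcome and the remedy is cheap.

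**What to change.** In the Data Analysis section:

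1. Limit the ANCOVA sentence to continuous scale scores.
2. Replace the count-model text with wording such as: *Unplanned admission counts, ED visits and provider visits will be analysed by negative binomial regression, with log time at risk (to death, withdrawal or 6 months) as offset and the baseline count as covariate.*
3. For clarity only, name 1-month readmission under the logistic model already planned for admissions.
4. State that patients who die contribute their visits and their time up to death, and report the rate ratio beside the mortality result. The offset corrects for length of observation, not for differences in who survives.

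The cost is wording and a little more analysis work. Each patient needs an end-of-follow-up date. Death and hospitalisation times are already needed for the planned survival analyses, but the documents do not say that withdrawal dates are recorded, so this should be confirmed. The look-back period for the baseline count should also be stated, since Table 1 does not give one.

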### **Aim 2.**

We aim to explore associations of outcome measures with certain patient characteristics to determine which patients benefit the most from each care model, considering important patient-centered characteristics such as function, HF severity, rurality, and other demographic characteristics; and considering location of caregivers, and HC system outcomes such as emergency department visits and readmissions.

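### Visit-specific subgroup effects depend on a significant whole-sample arm-by-time test, which does not test whether subgroup effects change between 3 and 6 months

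*Combined protocol and SAP*

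**What the plan says.** The Data Analysis section examines heterogeneity by adding a baseline-factor-by-arm interaction to the primary repeated-measures model. How time enters then depends on a test. Visit-specific subgroup effects are conditional: "If the arm x time interaction is significant, we will include 3-way interactions to investigate if the intervention effect differs by subgroup". In all other cases, "When there is not a significant interaction with time, we will investigate how the arm effect differs for subgroups averaged across time". The first of these sentences names the arm-by-time term, so the condition is the two-way interaction in the whole sample.

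The primary outcome has no such condition: "we will compare intervention effect at 3 months and at 6 months using contrasts", each at 0.025.

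On importance, the Data Analysis section says "Evaluating heterogeneity of the treatment effect is a key consideration for Aim 2 since we want to identify which patients benefit most". The Aim 2 section frames the work as exploratory: "We aim to explore associations of outcome measures with certain patient characteristics to determine which patients benefit the most from each care model".

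No significance level is given for the arm-by-time pre-test or for the subgroup tests. The planned sensitivity analyses cover distributional assumptions and missing data; none fits the three-way terms unconditionally.

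**The concern.** The pre-test answers a different question from the one it controls. Whether subgroup effects may be averaged over the two visits depends on whether the subgroups change differently between visits, which is the three-way term. The plan looks instead at whether the arm effect changes in the sample as a whole. A non-significant result there does not support averaging within subgroups.

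Two consequences follow. First, the subgroup quantity that is reported, visit-specific or averaged, is chosen by the data through a test that may have little power. Second, when the test is not significant, Aim 2 describes moderators of a time-averaged effect, while the primary analysis reports effects at 3 and at 6 months. A moderator acting mainly at one visit is then diluted.

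**Working it through.** The documents give no power figure for the subgroup analysis, so there is none to reproduce.

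**Algebra (no assumptions needed).** Let dA and dB be the change in arm effect from 3 to 6 months in subgroups A and B, and p the share in A.

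- Whole-sample arm-by-time term: p·dA + (1−p)·dB
- Three-way term: dA − dB

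The first can be zero while the second is large.

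**Inputs for the illustration.**
- N = 360: the target of 400 (Study Population) less the up to 10% who may die by six months (Data Analysis).
- p from 0.5 down to 0.2: the plan drops factors with subgroups below 20%.
- Assumed: 1:1 allocation, correlation ρ = 0.5 between visits, two-sided alpha 0.05 for every test, effects in SD units.

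**Standard errors.** Write k = (4/N)·(1/p + 1/(1−p)).
- Arm-by-time: √(2(1−ρ)·4/N) = √(4/360) = 0.105
- Subgroup difference at one visit: √k = 0.211 (p = 0.5), 0.230 (p = 0.3), 0.264 (p = 0.2)
- Subgroup difference averaged over visits: √((1+ρ)/2)·√k = 0.866·√k
- Three-way term: √(2(1−ρ))·√k, which equals √k at ρ = 0.5

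Power is approximately Φ(effect/SE − 1.96). The pre-test alone has 30% power for a 0.15 SD difference between the 3- and 6-month effects (0.15/0.105 = 1.42).

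**Case 1: 0.50 SD benefit in subgroup A at 6 months only.** The overall arm-by-time effect is 0.50p, the 6-month subgroup difference 0.50 and the averaged difference 0.25. The arm-by-time estimate is uncorrelated with the subgroup differences, so power under the plan's rule is P(significant)·(6-month power) + P(not significant)·(averaged power).

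| p | Pre-test significant | 6-month contrast | Averaged contrast | Plan's rule |
|---|---|---|---|---|
| 0.5 | 66% | 66% | 28% | 0.660×0.660 + 0.340×0.278 = 53% |
| 0.3 | 30% | 58% | 24% | 0.296×0.585 + 0.704×0.241 = 34% |
| 0.2 | 16% | 48% | 20% | 0.158×0.475 + 0.842×0.195 = 24% |

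A simulation of the rule gives the same figures.

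Sensitivity to ρ: the 6-month column does not change. At p = 0.5 the rule gives 0.518×0.660 + 0.482×0.313 = 49% for ρ = 0.3 and 0.865×0.660 + 0.135×0.251 = 60% for ρ = 0.7. At p = 0.2 it gives 0.126×0.475 + 0.874×0.218 = 25% and 0.232×0.475 + 0.768×0.177 = 25%.

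**Case 2, an extreme: equal halves with opposite patterns.** One half gains 0.30 SD at 3 months only, the other 0.30 SD at 6 months only. The overall arm-by-time effect and the averaged subgroup difference are both 0, so the pre-test is significant in 5% of trials. The three-way effect is 0.60: 0.60/0.211 = 2.85, power 81% (67% at ρ = 0.3, 96% at ρ = 0.7). Each per-visit contrast has only about 30% power (0.30/0.211 = 1.42).

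**Case 3: stable 0.50 SD subgroup difference, p = 0.5.** Averaged contrast: 0.50/0.183 = 2.74, power 78%. Per-visit contrast: 66%.

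**The case against.** Averaging over time when the arm effect does not detectably vary is a common, prespecified simplification. It has a real advantage: Case 3 shows that it is the more powerful analysis when a subgroup effect is stable. A subgroup analysis is done whichever way the pre-test falls, the aim is exploratory, and the primary contrasts are not touched. The plan lists ten moderators and leaves the list open, so unconditional per-visit contrasts add comparisons to an analysis with no stated multiplicity adjustment. If the 0.025 level of the primary contrasts were applied, the 66% for the direct 6-month contrast would fall to about 55%.

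All of this stands and limits the weight of the point. It does not rescue the pre-test. The advantage of averaging is kept if the averaged contrast is always reported, and a pre-test with no stated level does not control error across moderators.

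A reader might also set 66% against 28% in the first row of the table and infer a loss of 38 points. That is not what the plan does: 28% is the averaged test alone, whereas in that scenario the pre-test is significant in 66% of trials and the visit-specific contrast is then used. The loss at equal shares is about 13 points.

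**Conclusion.** The point holds as a minor one. The condition rests on the wrong term, whatever the numerical assumptions, and no other part of the documents removes it. For a late effect in one subgroup, the loss of power is about 13 points at a 50% share (66% to 53%) and about 24 points at a 30% share (58% to 34%) or a 20% share (48% to 24%). These sizes depend on the assumed 360 patients, 1:1 allocation, correlation, alpha and effect size.

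Two stronger readings are not supported. Case 2 might suggest that the rule generally hides subgroup effects almost completely; that needs equal and opposite patterns in equal halves, which nothing in the documents leads one to expect, and even without the pre-test each per-visit contrast would be weak. Nor does the text make subgroup findings a key consideration for the whole trial: it says so for Aim 2, which is exploratory.

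**What to change.** Delete the condition on the arm-by-time test. For each prespecified moderator:

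- fit arm by time by factor;
- report subgroup contrasts at 3 and at 6 months with confidence intervals, to match the primary contrasts;
- always report the time-averaged contrast as well, whatever the arm-by-time result.

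State the significance level used for the subgroup tests, label the results exploratory, and say that they will be interpreted with multiplicity in mind.

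The cost is a change of SAP wording and more table columns, with no new data, sample size change or change to the primary test. Per-visit intervals are about 15% wider than the averaged one (1/0.866 = 1.15), and each moderator yields three subgroup contrasts plus a three-way test, so there are more comparisons to interpret with care.

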Investigation of mediators (SCI-2) will be done by examining whether changes in self-care confidence, self-efficacy to manage symptoms, self-efficacy to manage

medications & treatment, or HF knowledge mediate the effect of the mHealth intervention on patient outcomes (e.g., self-care of HF index). We will use the method proposed by Hayes (2016) for evaluating mediation effects via a regression modeling approach which reflects the change scores in the mediators. Baseline measurement of the potential mediator and baseline outcome measure (e.g., self-care of HF index) will be included as covariates to provide a precise estimate of mediation effects. The test of mediation evaluating the indirect effect of the invention on outcome will be based on a product of coefficients approach. The modeling and testing for mediation as described by Hayes (2016) will be done for each mediator separately. As a sensitivity analysis for the mediation analyses, we plan to use a non-parametric bootstrap approach. Both the indirect effect of each mediator along with 95% bootstrap confidence intervals will be reported.

Sensitivity analyses to determine the impact of key assumptions. In the event that continuous endpoints are skewed or key distributional assumptions are not met, we will investigate transformations (e.g., log) and compare findings based on parametric and non-parametric tests (e.g., Wilcoxon rank-sum test & robust regression techniques), as a sensitivity analysis to confirm findings. To address the impact of missing data, multiple imputation methods will be investigated.

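### The mediation regressions name only two baseline-score covariates, which leaves the non-randomized mediator-to-outcome path open to confounding by characteristics the trial already measures

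*Combined protocol and SAP*

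**What the plan says.** The mediator paragraph of Data Analysis plans a separate regression-based mediation analysis for each of four candidates: self-care confidence, two self-efficacy scales and HF knowledge. Change scores represent the mediators. The covariates named are "Baseline measurement of the potential mediator and baseline outcome measure", which "will be included as covariates to provide a precise estimate of mediation effects". On inference it says: "The test of mediation evaluating the indirect effect of the invention on outcome will be based on a product of coefficients approach". The one sensitivity analysis specific to mediation is this: "As a sensitivity analysis for the mediation analyses, we plan to use a non-parametric bootstrap approach".

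Elsewhere the plan has more to draw on. The primary model is described as "adjusting for baseline subscale score and other covariates such as age, race, education, and rurality". Table 1 lists, at baseline, the SLUMS cognitive examination, the Newest Vital Sign ("Screens for Health Literacy"), HF severity from self-report and record review, and depression within the PROMIS 43 profile. The Aim 2 text lists HF severity and depression as candidate moderators. The mediator paragraph mentions none of these.

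**The concern.** Patients are randomized to an arm, not to a gain in knowledge or confidence. The arm-to-mediator coefficient is protected by design. The mediator-to-outcome coefficient is an observational association within arms, and it multiplies into every indirect effect. If, for example, better cognition leads both to larger knowledge gains and to larger self-care gains, the two gains will correlate even when knowledge does nothing for self-care.

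The two planned covariates are justified by precision. They do remove confounding that runs through the baseline scores, but not what acts on follow-up values beyond those scores. A bootstrap describes sampling error around whatever the model estimates, so a confounded slope receives an interval around the confounded value. The plan's other sensitivity analyses deal with distributional assumptions and missing data. At stake is whether Aim 3 reports a mechanism that is not there, or misjudges the size of one that is.

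**Working it through.** The plan gives no power, effect size or error rate for the mediation analysis, so there is no figure to reproduce. The check has two parts: how much confounding the planned covariates leave, and what that does to the test.

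**Inputs from the documents.** 400 patients (Study Population). Up to 10% may die by six months (missing-data paragraph of Data Analysis), so 400 × 0.90 = 360. Covariates and product-of-coefficients test as described above.

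**Assumed, not in the documents.** One standardized baseline confounder U, correlated 0.4 with baseline mediator M0 and baseline outcome Y0 (both SD 1). Follow-up mediator = 0.5·M0 + 0.3·arm + g·U + error. Follow-up outcome = 0.5·Y0 + b·(mediator change) + h·U + error. Error SD is σ. Here g and h are U's effects beyond the baseline scores.

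**Step 1: what the two covariates remove.** corr(M0, Y0) = 0.4 × 0.4 = 0.16. The share of U explained by M0 and Y0 is 2 × 0.4² / (1 + 0.16) = 0.32/1.16 = 0.276. The share left is v = 0.724.

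**Step 2: bias in the mediator-to-outcome slope.** Bias = g·h·v / (g²·v + σ²). The spurious indirect effect is 0.3 times that. With σ = 0.8 (σ² = 0.64), g = h and true b = 0:

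| g = h | Slope bias (formula) | Indirect effect | False mediation, two covariates | False mediation, U added |
|---|---|---|---|---|
| 0 | 0 | 0 | 5.6% | 5.6% |
| 0.1 | 0.0072/0.6472 = 0.011 | 0.003 | 5.2% | 4.8% |
| 0.2 | 0.0290/0.6690 = 0.043 | 0.013 | 12.4% | 4.6% |
| 0.3 | 0.0652/0.7052 = 0.092 | 0.028 | 36.4% | 4.0% |

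The last two columns are simulated: 2,000 trials per row, n = 360. False mediation means that a 95% Monte Carlo interval for the indirect effect, used in place of the bootstrap, excludes zero. The simulated mean slopes (0.011, 0.044, 0.092) agree with the formula. Simulation error near 5% is √(0.05 × 0.95/2000) = 0.5 percentage points. At n = 400 the two-covariate rates are 4.9%, 4.4%, 12.6% and 39.2%, so a larger sample gives no relief.

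**Step 3: range.** A larger residual spread dilutes the bias. At g = h = 0.3 and σ = 1.0 it is 0.0652/1.0652 = 0.061 instead of 0.092. Keeping the 0.4 correlation and letting σ run from 1.0 to 0.8, false mediation is near nominal at 0.1, about 5–13% at 0.2, 15–38% at 0.3 and 35–74% at 0.4. With U in the model it is 2–5%. This is not an upper bound: if U were unrelated to the baseline scores (v = 1), the bias at 0.3 with σ = 0.8 would be 0.09/0.73 = 0.123.

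**Step 4: a real mediator effect.** With true b = 0.20 and σ = 0.8, the two-covariate model estimates 0.20, 0.21, 0.24 and 0.29 at g = h = 0, 0.1, 0.2 and 0.3. With U added it estimates 0.20 throughout.

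**Step 5: direction.** The bias takes the sign of g·h. With g = 0.3 and h = −0.3 it is −0.092, and a true 0.20 would be estimated at about 0.20 − 0.092 = 0.108.

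**The case against.** The strongest reply is that the two baseline scores already do much of the work. If cognition, literacy, depression and severity act mainly through where a patient starts, little bias is left, as the 0.1 row shows. The size also depends on how a confounder effect is read. If 0.2, 0.3 and 0.4 are total associations, including the part that runs through baseline, the two-covariate model gives false mediation of 5%, 5% and 12% when the confounder–baseline correlation is 0.4, and 3%, 7% and 31% when it is 0.3. Nothing in the documents shows that any of the four characteristics predicts change once baseline scores are held. This stands, and it limits the point to exposure to bias.

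The direction is also open. Patients with low literacy may start low and have more room to gain knowledge, which could weaken or reverse an association. This stands too.

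The mediator paragraph does not expressly exclude other covariates, and the primary-model list is given by example. But a reader following the mediator paragraph as written would fit two covariates. The clause on adjusting for baseline imbalance does not help: it concerns differences between arms, and a perfectly balanced variable can still confound mediator and outcome.

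Finally, the benefit of adjustment shown above assumes that the confounder is known and well measured. Real covariates will do less.

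**Conclusion.** The concern holds as a gap in specification. The slope on which every indirect effect depends is left open to confounding by four characteristics measured at baseline, and no planned analysis would reveal it. The possible inflation runs from none to large, and the figures rest on an assumed single confounder acting in the same direction on mediator and outcome.

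A reader might infer that the path is in fact confounded, or that the indirect effects will be biased away from zero. The documents support neither: they give no confounder strengths, the baseline-score adjustment blocks part of the problem, and opposite-sign effects would bias the other way. A reader might also infer that the trial's main result is in doubt. It is not, because the arm contrast is randomized and Aim 3 is framed as exploratory. The change is still worth making, since Aim 3 is one of three stated aims and its results will be read as explaining how the intervention works.

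**What to change.** In the mediator paragraph of Data Analysis, prespecify one set of baseline covariates, to be used in both the mediator and the outcome regression for every candidate mediator. A reasonable set is the baseline mediator and outcome already named, the primary-model covariates (age, race, education, rurality), SLUMS, Newest Vital Sign, HF severity and PROMIS depression. Other Table 1 items could be argued for. What matters is that the set is fixed before outcome data are analysed by arm.

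Add a sensitivity analysis that reports, for each mediator, the residual mediator–outcome correlation that would bring the indirect effect to zero. State that unmeasured and post-randomization confounding remain possible, and say which visit's mediator change is paired with which visit's outcome, since the paragraph leaves the time order open.

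The cost is a few sentences of SAP text and a few degrees of freedom. No new data are needed.
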